4.4.5 Breaking the Treatment Code by the Sponsor

The Sponsor may break the treatment code for subjects who experience a Suspected Unexpected Serious Adverse Reaction (SUSAR), in order to determine if the individual case or a group of cases requires expedited regulatory reporting. Individual Emergency Code will be provided to the limited staff who are empowered to break the codes for all SUSAR cases for reporting purposes.

4.5 Assignment and Allocation

After a subject signs informed consent, a subject number will be assigned. To obtain a subject number, the Investigator or designee will utilize a web or phone-based Interactive Response Technology (IRT), available seven days a week and 24 hours a day.

Subjects who meet all the inclusion and none of the exclusion criteria will enter a 2-week placebo run-in period (Visit 2). At Visit 3 (Baseline), subjects will be randomly assigned to receive 25 mg mirabegron or placebo using a 1:1 randomization schedule.

To obtain the randomized treatment, the Investigator or designee will utilize a web or phone-based IRT, available seven days a week and 24 hours a day. After submitting certain information about the eligible subject, the randomized drug assignment will be provided by the IRT. Study drug assignment will remain blinded to all staff. Study drug will be packaged in bottles. Each study drug bottle will be preprinted with a Medication ID number. The Medication ID number assigned to the subject will be noted in the electronic case report form (eCRF) for study drug.

Once a subject number is assigned, if the corresponding subject does not receive study drug, the subject number will not be used again.

5 TREATMENTS AND EVALUATION

5.1 Dosing and Administration of Study Drugs and Other Medications

5.1.1 Dose/Dose Regimen and Administration Period

Subjects will be randomized to one of two treatment groups in a 1:1 ratio to either mirabegron or placebo (PBO). Randomization will be stratified by age < 75 years and ≥ 75 years. Those subjects randomized to mirabegron will start at 25 mg and may increase to 50 mg after 4 weeks or 8 weeks based on individual subject efficacy, tolerability and Investigator discretion. Those subjects randomized to PBO will start blinded product matched to the mirabegron 25 mg tablet and may also increase to 50 mg PBO after 4 or 8 weeks. Once a patient has increased dose, they will remain on that dose for the remainder of the study unless for safety reasons that require discontinuation of study drug.

5.1.2 Previous and Concomitant Medication (Drugs and Therapies)

5.1.2.1 Previous Medication (Drugs and Therapies)

The Investigator must record the use of previous (all medication taken within 30 days prior to Screening (Visit 1)) and current concomitant treatment, both drug and non-drug therapies, prescribed and over-the-counter and all alternative medicines, in the eCRFs. This also includes drugs used on a chronic and as-needed basis.

Subjects must be instructed not to start any new medication, both prescribed and over-the-counter, without consulting the Investigator, unless the new medication is required for emergency use. Subjects must be instructed to notify the Investigator immediately if medications were required for emergency use.

5.1.2.2 Concomitant Medication (Drugs and Therapies)

Concomitant medications will be captured from Screening (Visit 1) through the Follow-up Phone Call (Visit 7/Week 16).

Prohibited Medications

Medications prohibited between Screening (Visit 1) and Week 12/End of Treatment (Visit 6) include anticholinergics, antispasmodics, and CYP2D6 substrates with narrow therapeutic index (see [Appendix 1](#) Part A). These medications must have been discontinued at least 30 days prior to Screening (Visit 1). Current or previous use of mirabegron at any time is prohibited. This list is not inclusive of all possible prohibited medications. In case of doubt, the Investigator must contact the local study monitor.

Restricted Medications

Medications restricted between Screening (Visit 1) and Week 12/End of Treatment (Visit 6) include loop diuretics, alpha blockers and 5-Alpha reductase inhibitors. All medications in Part B of [Appendix 1](#) are permitted provided the subject has been taking this medication on a long-term basis, i.e., has not stopped, or started or changed dose within the 30 days prior to Screening (Visit 1), no new drug of the same class has been added to the regimen within the

30 days prior to Screening (Visit 1), and the subject remains on the medication at the same dose during the course of the study.

Restricted Non-Drug Therapy

Subjects participating in any behavioral modification therapy (i.e., pelvic floor exercises, Kegel exercises, biofeedback, timed voiding, etc.) or other non-drug therapy must have started the therapy at least 30 days prior to Screening (Visit 1) and must continue the same schedule through Week 12/End of Treatment (Visit 6).

5.1.3 Treatment Compliance

Study subjects should be counseled on the need to meet 100% compliance with study drug. Investigator or designee should ensure that study subjects meet this goal throughout the study period. Compliance will be verified by the accounting of study drug at each monthly visit after baseline. When study drug is administered at the research facility, it will be administered under the supervision of study personnel.

Compliance of the study drug will be monitored by the accounting of unused medication returned by the subject at visits. Compliance will be documented.

If compliance is less than 80% or more than 120%, the Investigator or designee is to counsel the subject and ensure steps are taken to improve compliance. Subjects who are less than 80% or more than 120% compliant with the dosage regimen for any two consecutive visit periods during the study should be withdrawn from the study.

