2. Subject was non-compliant during 2-week placebo run-in period, defined as taking less than 80% and greater than 120% of study medication.
3. Subject has any systolic blood pressure measurement \geq 180 mmHg or diastolic blood pressure measurement \geq 110 in the 3-day diary or during the baseline visit.

Waivers to the exclusion criteria will NOT be allowed.

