5.4.3 Montreal Cognitive Assessment

Montreal Cognitive Assessment (MoCA) will be assessed at Baseline (Visit 3) and Week 12/End of Treatment (Visit 6).

The MoCA was designed as a rapid screening instrument for mild cognitive dysfunction. It assesses different cognitive domains: attention and concentration, executive functions, memory, language, visuoconstructional skills, conceptual thinking, calculations, and orientation. Time to administer the MoCA is approximately 10 minutes. The total possible score is 30 points [Nasreddine et al, 2005].

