7 STATISTICAL METHODOLOGY

The statistical analysis will be coordinated by the responsible biostatistician of Astellas. A Statistical Analysis Plan (SAP) will be written to provide details of the analysis. In addition, specifications for tables, listings, and figures will be produced. The SAP will be finalized before database softlock at the latest. Any deviations from the analysis planned in SAP will be justified in the Clinical Study Report.

Prior to database lock, a Final Review of Data and TLFs meeting will be held to allow a review of the clinical trial data and to verify the data that will be used for analysis set classification. If required, consequences for the statistical analysis will be discussed and documented. A meeting to determine analysis set classifications may also be held prior to database hard lock.

In general, baseline is defined as the last measurement before the first dose of double-blind study drug. For variables based on the micturition diary, the 3 days of the diary recorded prior to the baseline visit will be used to derive these variables at baseline just as the 3 diary days before each post-baseline visit will be used to derive these variables at these visits.

The End of Treatment (EOT) visit is defined as the last post-baseline visit at the end of the double-blind treatment period for which data is available. The EOT visit value for diary variables is the average or number of the diary measurements for Week 12, as applicable. If no Week 12 diary data measurements are available, then the last available earlier post-baseline average or number of the diary measurements within a designated visit window will be used.

All statistical comparisons will be made using a two-sided test at $\alpha = 0.05$ significance level and confidence intervals will be reported with a coverage consistent with this significance level. Efficacy and safety variables will be summarized using descriptive statistics. Continuous variables will be summarized using mean, standard deviation (SD) or standard error (SE), minimum, median, maximum unless specified otherwise. Categorical variables will be described using absolute and relative frequency.

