7.10 Handling of Missing Data, Outliers, Visit Windows, and Other Information

For efficacy variables and vital sign data, analysis at End of Treatment will take into account subjects who withdraw before Week 12 and therefore do not have measurements available for that visit. The End of Treatment analysis is a LOCF (last observation carried forward) approach.

Other imputation rules to account for missing data will be described in the SAP.

Subjects do not always adhere strictly to the visit timing in the protocol. Visit windows around the target days for each visit will be defined in the SAP.

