5.2.1 Reasons for Exclusion From PPS

The following criteria listed in Table 3 may lead to subject's exclusion from PPS.

Table 3. Criteria for Assessing Major Protocol Violations which could potentially Impact Efficacy Assessments

Number	MPV Criteria
Treatment Violations	
1	Double Blind treatment duration of less than 53 days
2	No measurement of the primary efficacy endpoint available at or after Visit 2
3	Treatment compliance of less than 70% between randomization and last visit
4	Administration of excluded concomitant treatment as described in the Study Protocol.
Inclusion Criteria Violations	

5	Subject did not experience at least one incontinence episode based on the 3-day micturition diary at baseline.
6	Subject did not experience at least 3 episodes of urgency (grade 3 or 4) based on the 3-day micturition diary at baseline.
7	Subject did not experience an average of greater than or equal to 8 micturitions/day based on the 3-day micturition diary at baseline.
Exclusion Criteria Violations	
8	Subject was non-compliant during 2-week placebo run-in period, defined as taking less than 80% or greater than 120% of study medication
9	Subject did not complete all 3 days of the baseline 3-day micturition diary
10	Unblinding of Study Drug
11	Error in Study Drug Administration
Other Exclusions from PPS	
12	Subject did not complete at least 2 days of the EOT 3-day micturition diary

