7.1.1 Last Observation Carried Forward (LOCF)

For the efficacy diary data the EoT value will be calculated as the average or the count of the valid diary measurements reported in the last 3 valid diary days of the analysis visit window prior to EoT. For subjects who withdraw before week 12, the last available post-baseline average of the diary data measurements will be carried forward as the EoT value (LOCF).

For the non-diary efficacy data and safety data, the EoT value will be the last measurement within the week 12 visit day windows. For subjects who withdraw before week 12 the last measurement within the analysis visit window of the last available post-baseline visit will be carried forward as the EoT value (LOCF).

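### Withdrawing poor compliers from the study (protocol 5.1.3) can replace an obtainable Week 12 diary with LOCF; separately, nothing requires the only post-baseline MoCA, laboratory and PVR tests at early withdrawal

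*Protocol*

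**What the plan says.** Under protocol 5.1.3, tablets are counted at each monthly visit after baseline. After one period outside 80-120%, "the Investigator or designee is to counsel the subject and ensure steps are taken to improve compliance". Subjects outside those limits "for any two consecutive visit periods during the study should be withdrawn from the study". The verb is *should*, and the object is the study, not study drug. Section 6.1 separates leaving treatment from leaving the study. It does not list non-compliance among the mandatory reasons for discontinuation, and it places lack of cooperation among the discretionary ones. The same 80-120% limits act as an exclusion before randomization (section 3.3: "Subject was non-compliant during 2-week placebo run-in period").

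For missing outcomes, protocol 7.10 applies LOCF to "subjects who withdraw before Week 12 and therefore do not have measurements available for that visit". SAP 7.1.1 adds that "the last available post-baseline average of the diary data measurements will be carried forward as the EoT value". SAP 7.10.3.1 discards diary days more than 7 days after the last double-blind dose.

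MoCA (protocol 5.4.3), laboratory tests (5.4.5, 5.8) and PVR (5.4.8) each have one scheduled post-baseline assessment, at Week 12/End of Treatment. Section 7 says that the End of Treatment visit "is defined as the last post-baseline visit at the end of the double-blind treatment period for which data is available". Neither section 6.1 nor the Schedule of Assessments provides an early-termination visit.

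The SAP also deals with compliance through the per-protocol set. One criterion for possible exclusion (SAP 5.2.1, Table 3) is "Treatment compliance of less than 70% between randomization and last visit".

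**The concern.** Compliance after randomization can depend on how well the drug works and how well it is tolerated. A rule that ends study participation on that basis creates missing Week 12 data selectively, where the data could have been collected. A subject who takes three quarters of the tablets can still fill in a diary, and the treatment-as-assigned comparison in FAS-I would want that diary. Protocol 7.8 and 8.1.6 add pressure: keeping a subject who has met a withdrawal criterion can be read as deviation PD2, which must be notified to the sponsor.

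The second point concerns safety. LOCF cannot help MoCA, laboratory tests or PVR unless a post-baseline value has been taken, and the only scheduled one is at Visit 6. Protocol 1.1 presents this as the first study to explore mirabegron and cognition in older adults, and SAP 7.5 keeps MoCA as its one inferential safety comparison.

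**Working it through.** **The plan's own figures.** Counting ties as one half, protocol Table 4 gives P(mirabegron better) = 0.563, as stated. Noether's formula at 340 per arm gives 81.2% power with P = 0.563 and 81.5% with the unrounded P (stated 82%). The micturition comparison (0.796, SD 2.7) gives 97.0% (stated 97%). 340/0.85 = 400. The sample size is not in question.

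**When the rule costs data.** A subject non-compliant in the run-in is not randomized, so the first two double-blind periods that can both fail are Baseline-Week 4 and Weeks 4-8, found at Week 8. The Week 12 diary is then lost and normally the Week 8 value is carried forward. If the failing periods are Weeks 4-8 and 8-12, the failure is found at Week 12 and no diary is lost.

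**Size for micturitions.** Assumptions, none from the documents: 1-5% of one arm withdrawn at Week 8, and carried-forward values that differ from the true Week 12 values by 0.4-1.0 per 24 h.
- Shift = fraction x discrepancy: 0.01 x 0.4 = 0.004; 0.05 x 1.0 = 0.050.
- SE of the difference = 2.7 x sqrt(2/340) = 0.207.
- 0.004/0.207 = 0.02 SE; 0.050/0.207 = 0.24 SE.
- Against the planned effect: 0.004/0.796 = 0.5%; 0.050/0.796 = 6.3%.

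**Size for incontinence.** Assume that 1-5% of the mirabegron arm, spread over Table 4 in proportion, moves by one category.
- One category worse: P changes by -0.0013 to -0.0064.
- One category better: P changes by +0.0011 to +0.0056.
- SE of P = sqrt(681/(12 x 340^2)) = 0.0222.
- That is 0.06-0.29 SE if worse and 0.05-0.25 SE if better.

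Both ranges put all the withdrawals in one arm. Equal effects in the two arms give no shift.

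**Safety data.** The same assumed 1-5% of 400 is 4-20 subjects per arm. The planned 15% dropout from all causes is 0.15 x 400 = 60 per arm, which is 60/20 = 3 to 60/4 = 15 times as many. The gap therefore belongs mainly to early withdrawal in general.

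**Would stopping drug without leaving the study restore the diary?** By the protocol schedule, Week 8 falls no later than Day 63 (56 + 7) and Week 12 no earlier than Day 77 (84 - 7). Even then the first diary day comes 77 - 3 - 63 = 11 days after a last dose taken at the Week 8 visit. That is past the 7-day limit, so a subject taken off drug at Week 8 still has LOCF in the primary analysis. Only subjects kept on drug gain an observed primary value.

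**The case against.** The strongest reply is that exposure is narrow and the effect negligible. Non-compliers are screened out in the run-in, counselling follows any failing period, the rule leaves discretion, and the Week 8 diary is still collected. Protocol 2.2.2 says that the Week 4 effect approaches the maximum, so a Week 8 value should be close to Week 12. The 1.0 discrepancy used above exceeds the whole planned effect of 0.796. All of this stands, and it is why no material bias is claimed.

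Some stronger readings are tempting, but the documents do not support them.
- *Section 5.1.3 costs power.* LOCF keeps these subjects in FAS-I, and some of them may already be within the 15% dropout.
- *Section 5.1.3 is what loses the safety data.* Any early withdrawal has the same consequence. The loss is also not certain: Visit 6 carries the End of Treatment label, so a site might do the tests at withdrawal, and SAP 7.1.1 would carry a Week 8 result forward. Vital signs and ECG are available from Weeks 4 and 8 in any case.
- *The 80% limit contradicts the 70% limit for the PPS.* A subject taking 20-22 tablets in each 28-day period (71-79%) falls between the two. However, 80% is a conduct rule applied period by period, while 70% is a cumulative criterion for an analysis set, and it only may lead to exclusion. The PPS also requires completion of the study, so someone withdrawn at Week 8 fails it anyway. The two limits serve different purposes and are not inconsistent.

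What remains is that the rule discards obtainable outcomes for little visible gain, and that no text requires end-of-treatment tests when a subject leaves early.

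**Conclusion.** The point holds as a cheap improvement in two separate parts. First, 5.1.3 can turn an obtainable Week 12 diary into a carried-forward one for subjects selected on post-randomization behaviour. The number and the direction are unknown. On assumed rates of 1-5% in one arm, the shift is 0.02-0.24 SE for micturitions and 0.05-0.29 SE for incontinence, so the effect on the co-primary results is probably small. Second, the only scheduled post-baseline MoCA, laboratory and PVR results may be lost at early withdrawal for any reason. That covers an assumed 4-20 subjects per arm under the compliance rule, and up to about 60 per arm at the planned 15% dropout if sites do not do the tests on leaving. The second part has the wider reach and does not depend on the compliance rate.

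**What to change.** - Amend 5.1.3, and align 6.1 with it, so that under-compliance leads to counselling while the subject stays on drug and on scheduled visits. Above 120%, stop drug only where safety requires it, without study withdrawal.
- State in 7.8 and 8.1.6 that keeping a non-compliant subject is not a PD2 deviation.
- Handle non-compliance through the PPS. SAP Table 3 has a lower compliance limit after randomization but no upper one, so add an upper limit if taking more than 120% is to count.
- Require the Visit 6 MoCA, laboratory and PVR procedures at any early withdrawal, whatever the reason.
- Keep the SAP 7-day diary rule for the primary analysis. Optionally, add a sensitivity analysis using off-drug Week 12 diaries, applied to all discontinuers alike.

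The cost is wording in 5.1.3, 6.1 and the PD2 definition, plus one line on procedures at early withdrawal. It adds no new type of visit or test. The downside is that some FAS-I data will come from poor compliers.

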5.1.4 Emergency Procedures and Management of Overdose

Mirabegron has been administered to healthy volunteers at single doses up to 400 mg. At this dose, adverse events reported included palpitations (1 of 6 subjects) and increased pulse rate exceeding 100 bpm (3 of 6 subjects). Multiple doses of mirabegron up to 300 mg daily for 10 days showed increases in pulse rate and systolic blood pressure when administered to healthy volunteers. Treatment for overdosage must be symptomatic and supportive. In the event of overdosage, pulse rate, blood pressure and ECG monitoring is recommended.

5.2 Demographics and Baseline Characteristics

5.2.1 Demographics

The subject's date of birth, sex, race, ethnicity, height, and weight will be recorded at Screening (Visit 1).

5.2.2 Medical History

Medical history (other than for overactive bladder), including smoking history will be obtained at Screening (Visit 1) from each subject. All relevant past and present conditions, as well as prior surgical procedures will be recorded for the main body systems.

5.2.3 Diagnosis of the Target Disease, Severity, and Duration of Disease

A detailed OAB history for each subject will be obtained at Screening (Visit 1).

5.3 Efficacy

5.3.1 Patient Diary - Micturition and Incontinence

During the study, subjects will be requested to complete a 'Subject diary' which will be implemented on an electronic handheld device. This diary will collect data on micturition and incontinence. The information from the diaries will be used to evaluate the efficacy of treatment. Therefore, subjects will receive full instructions and training on how to complete the diary at Visit 2 (Placebo Run-In) and will be counseled on the importance of completing the diaries prior to the next visit. The training diary will be reviewed with the subject by the Investigator or designee to ensure accuracy and completion. The diaries and questionnaires will be reviewed during each visit after Visit 2 (Placebo Run-In) by the Investigator or designee to ensure accuracy of completion.

Diaries will be completed 3 consecutive days prior to each visit: Baseline (Visit 3), Week 4 (Visit 4), Week 8 (Visit 5), and Week 12/End of Treatment (Visit 6). During this activity, the subject will not come to the clinic for a visit. Site staff will contact the subject 3 days prior to the scheduled Visit to remind the subject they need to complete the electronic diary, review completion instructions and review changes to concomitant medications and adverse events (if applicable).

A diary day starts at midnight and ends at midnight the following day. Time to bed with intention to sleep, time to awake with intention of staying awake, type of episode (urination/incontinence), time of episode, urgency severity (see Section 5.3.4), measure of urine volume voided, and sleep interruption will be recorded by the subject in the micturition diary.

At Visit 3, diary data, including the frequency of micturition (urination episodes) urgency episodes (grade 3 and 4) and incontinence episodes per 24 hours, will be reviewed to confirm inclusion criteria.

Micturitions will be counted as only urination episodes and not episodes of incontinence.

In addition to the micturition information, the electronic diary will also collect time of medication intake.

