6.1.3.1 Patient Diary - Micturition and Incontinence

During the study, subjects will be requested to complete a ‘Subject diary’ which will be implemented on an electronic handheld device. This diary will collect data on micturition and

incontinence. The information from the diaries will be used to evaluate the efficacy of treatment. Therefore, subjects will receive full instructions and training on how to complete the diary at Screening (Visit 1) and will be counseled on the importance of completing the diaries prior to the next visit. The training diary will be reviewed with the subject by the Investigator or designee to ensure accuracy and completion. The diaries and questionnaires will be reviewed during each visit after Screening (Visit 1) by the Investigator or designee to ensure accuracy of completion.

Diaries will be completed 3 consecutive days prior to each visit: Baseline (Visit 3), Week 4 (Visit 4), Week 8 (Visit 5), and Week 12/End of Treatment (Visit 6).

A diary day starts at midnight and ends at midnight the following day. Time to bed with intention to sleep, time to awake with intention of staying awake, type of episode (urination/incontinence), time of episode, urgency severity, and sleep interruption will be recorded by the subject in the micturition diary.

At Visit 3, diary data, including the frequency of micturition (urination episodes), urgency episodes (grade 3 and 4) and incontinence episodes per 24 hours, will be reviewed to confirm inclusion criteria.

Micturitions will be counted as only urination episodes and not episodes of incontinence.

In addition to the micturition information, the electronic diary will also collect time of medication intake.

Definitions of efficacy variables based on the 3-day micturition diary are presented in Table 4.

Table 4. Micturition Diary Definitions and Calculations

Measurement	Definition	Calculation
Micturition	Any voluntary micturition (excluding incontinence only episodes).	A micturition episode is counted as micturition regardless of whether volume voided was recorded or not. A micturition recorded before midnight of the first day or after midnight on the 3rd day of the 3-day micturition diary period will not be counted. A micturition will also be counted if the subject assessed an episode as both micturition and incontinence.
Valid Diary Day	A diary day in which at least one voluntary micturition	A diary day is considered valid if at least one

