	episode occurs. A diary day with episodes of incontinence only is not considered a valid diary day.	micturition was recorded on this calendar day. Days of visits to the clinic (determined by the date of questionnaire completion) will not be counted as valid diary days.
Number of Valid Diary Days	Number of valid diary days per each 3-day micturition diary period.	Count of the valid diary days during the 3-day micturition diary period. Days of visits to the clinic will not be counted as valid diary days.
Valid Diary	A valid diary is a diary with at least 2 valid diary days within the analysis visit window. If more than 3 valid diary days are recorded then the last 3 days will be used in the calculations.	Not applicable.
Mean Number of Micturitions per 24 hours	Average number of times a subject urinates (excluding incontinence only episodes and excluding duplicate records [same time and episode characteristics]) per day during the 3-day micturition diary period.	Number of micturitions recorded on valid diary days during the 3-day micturition diary period divided by the number of valid diary days during the 3-day micturition diary period.
Urinary Incontinence Episode or Incontinence Episode	The complaint of any involuntary leakage of urine.	An incontinence episode is counted if it was recorded in the diary on a valid diary day. An incontinence will also be counted if the subject assessed an episode as both micturition and incontinence.
Number of Incontinence Episodes	Number of times a subject records an incontinence episode during the 3-day micturition diary period.	Total number of incontinence episodes recorded during the 3-day micturition diary period.
Mean Number of Incontinence Episodes per 24 hours	Average number of times a subject records an incontinence episode per day during the 3-day micturition diary period.	Number of incontinence episodes recorded on valid diary days during the 3-day micturition diary period divided by the number of

		valid diary days during the 3-day micturition diary period.
Mean Volume Voided per Micturition	Mean volume voided (mL) per micturition during 3 days of the 3-day micturition diary period.	Sum of each volume voided for each record with volume voided > 0 on valid diary days divided by the total number of records with a volume voided > 0 on valid diary days during 3 days with volume measurements in the 3-day micturition diary period.

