7.10.3.1 Analysis Visit Windows for Efficacy and Safety Variables

All the efficacy and safety assessments for a treatment period will be allocated based on the tables below.

Efficacy:

Analysis visit	Target day	Actual assessment day
Screening	Day -28	-38 to -18
Placebo Run-In	Day -14	-17 to 0
Baseline	Day 1	Day 1 ^a
Week 4	Day 30	15-42
Week 8	Day 60	43-70
Week 12/End of Treatment	Day 90	71-98
Follow Up Phone Call	Day 120	EOT+14

After Placebo Run-In, visit windows/study days will be calculated based on the Baseline (Visit 3) date.

Safety:

Analysis visit	Target day	Actual assessment day
Screening	Day -28	-38 to -18
Placebo Run-In	Day -14	-17 to 0
Baseline	Day 1	Day 1 ^a
Week 4	Day 30	2-45
Week 8	Day 60	46-75
Week 12/End of Treatment	Day 90	76-97
Follow Up Phone Call	Day 120	EOT+14

1. After Placebo Run-In, visit windows/study days will be calculated based on the Baseline (Visit 3) date.

For efficacy variables recorded in the 3-day micturition diary, the following rules will apply:

1. As micturition diary data are to be recorded from midnight 3 days prior to a visit to midnight 1 day prior to a visit, micturition diary records which have the same date as a visit date should be excluded from the analysis. Non-micturition questionnaire assessment dates will be compared to the eDiary dates and used to flag which diary records should be excluded.
2. Any diary days which are > 7 days after the last dose of double-blind treatment will not be included in the analysis.
3. Average values or number of episodes for count data will only be calculated if at least 2 valid diary days are available within the specified window. In the case that only 1 valid diary day is available, then no value will be calculated.
4. If there are more than 3 valid diary days available for a visit, the average will be based on the last 3 days prior to the scheduled visit.
5. Duplicate records (same time and episode characteristics) per day during the 3-day micturition diary period will be excluded.

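### The diary reminder is made after diary Day 1 has begun, so a subject who starts only when reminded gives a partial first day that the SAP scores as a full 24 hours

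*Protocol*

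**What the plan says.** **Reminder.** Protocol 5.3.1 and Table 1 footnote i state that "Site staff will contact the subject 3 days prior to the scheduled Visit to remind the subject they need to complete the electronic diary". The same contact goes over the completion instructions. It precedes Visits 3, 4, 5 and 6.

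**Diary days.** Protocol 5.3.1: "Diaries will be completed 3 consecutive days prior to each visit", and "A diary day starts at midnight and ends at midnight the following day". SAP 7.10.3.1 sets the window in the same way ("As micturition diary data are to be recorded from midnight 3 days prior to a visit to midnight 1 day prior to a visit") and adds that "micturition diary records which have the same date as a visit date should be excluded from the analysis".

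**Scoring.** SAP 6.1.3.1, Table 4: "A diary day is considered valid if at least one" "micturition was recorded on this calendar day". No minimum hours or start time is required. The mean per 24 hours is the "Number of micturitions recorded on valid diary days during the 3-day micturition diary period divided by the number of valid diary days"; incontinence is scored in the same way. Two valid days are enough for a visit value.

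**Safeguards.** Table 1 schedules diary instruction at Visits 2 to 6. Footnote g tells subjects in advance to begin 3 days before each visit and provides device training at Visit 2. Footnote j and Protocol 5.3.1 require diary review at each visit, and Protocol 8.1.1 adds review of the uploaded data while the subject is at the site.

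**The concern.** A reminder is useful only if it arrives before the thing it prompts. This one is dated on diary Day 1, which began at midnight. A subject who followed the advance instruction is unaffected. A subject who had forgotten and begins on being contacted has nothing recorded for the earlier part of that day, unless those episodes are entered afterwards.

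The SAP cannot tell that day from a complete one. It scores it as 24 hours with few episodes, and no rule detects, drops or pro-rates it. The per-protocol criteria in SAP 5.2.1 (Table 3, items 9 and 12) ask whether diary days were completed, and the only definition of a usable day is the one-micturition rule.

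Both co-primary endpoints come from this diary. So do the Visit 3 entry thresholds (an average of at least 8 micturitions/day, at least 3 urgency episodes of grade 3 or 4, at least 1 incontinence episode), the FAS-I requirement of a baseline incontinence episode, the responder endpoints, and nocturia, which would lose the night at the start of Day 1.

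**Working it through.** **1. Calendar.** Let V be the visit date. Visit-date records are excluded, so the three usable days are V−3, V−2 and V−1. The SAP words the end of the window loosely, but only 00:00 on V−3 to the end of V−1 gives three full days. The contact falls on V−3. At whatever hour it is made, Day 1 has started.

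**2. Effect on one diary.** Let B be the true daily count and f the share of Day 1 episodes missed. The SAP divides by 3 valid days, so

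recorded mean = (3B − fB)/3 = B(1 − f/3).

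The documents give no value for f, so a range is assumed:

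| f | Under-count | B = 8 | B = 10 | B = 12 |
|---|---|---|---|---|
| 0.20 | 6.7% | −0.53 | −0.67 | −0.80 |
| 0.35 | 11.7% | −0.93 | −1.17 | −1.40 |
| 0.50 | 16.7% | −1.33 | −1.67 | −2.00 |

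**3. The plan's own power figure.** Protocol 7.1: 340 per arm, difference 0.796, SD 2.7, two-sided 0.05. Recomputed power is 97.0%, which matches the stated 97%.

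**4. Illustration by start time (assumed void pattern).** Take 11 voids per 24 hours, 2 of them between 00:00 and 06:00 and 9 spread evenly over the next 16 hours.

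- Missed voids = 2 + (start hour − 6) × 9/16.
- Start at 09:00: 3.69 missed, and 3.69/3 = 1.23 per 24 hours too low.
- Start at 11:00: 4.81 missed, and 4.81/3 = 1.60 per 24 hours too low.

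**5. Power with 30% late starters (assumed, independent at each visit).** With b the under-count, the SD of the change becomes √(2.7² + 2 × 0.3 × 0.7 × b²).

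- b = 1.23: √(7.29 + 0.63) = 2.815; power 95.8%.
- b = 1.60: √(7.29 + 1.08) = 2.893; power 94.8%.

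This keeps the difference at 0.796. If the loss is proportional to the count, the difference also shrinks, to 0.796 × (1 − qf/3), where q is the share starting late. The added variance is then q(1 − q)(f/3)²(11² + 9.5²), for assumed means of 11 at baseline and 9.5 at end of treatment:

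| f | q = 25% | q = 50% | q = 100% |
|---|---|---|---|
| 0.20 | 96.2% | 95.5% | 94.8% |
| 0.35 | 95.0% | 93.2% | 92.4% |
| 0.50 | 93.0% | 89.5% | 89.3% |

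The lowest figure needs every subject to start late and lose half of Day 1.

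**6. Thresholds.** With a partial baseline diary, a subject must truly average 8/(1 − f/3) to record 8: that is 8.6, 9.1 or 9.6 for the three values of f. For example, a true 9.0 per day with 2 night voids and a 10:00 start misses 2 + 4 × 7/16 = 3.75 voids. It reads (27 − 3.75)/3 = 7.75 and fails entry. For incontinence, one missed leak moves the 3-day mean by 1/3 = 0.33. If it was the only leak in the diary, the subject fails entry at baseline or counts as a zero-incontinence responder afterwards. No power loss was computed for incontinence.

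**The case against.** The effect depends on subjects departing from a written instruction. They are told beforehand when to begin, trained at Visit 2, given a training diary that is reviewed, and have each diary reviewed with them at the site. The contact is a reminder, not a start signal, and nothing in the documents shows that subjects wait for it. Its hour is not stated. Subjects record the time of each episode, and the documents do not say that earlier episodes cannot be entered later. The SD of 2.7 comes from earlier trial data, so it may already contain some diary error of this kind.

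All of that stands, and it keeps the point conditional and small. It does not close the gap. Review at the visit can reveal a late start and prompt re-instruction, but it cannot restore unrecorded episodes, and the scoring rule still treats the day as complete.

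A reader might infer two stronger things that the documents do not support.

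- **That the treatment comparison is biased.** The previous instruction is 11 to 17 days old at baseline and about 4 weeks old afterwards, so late starts could be more common after baseline and look like improvement. The documents give no rates. The procedure is the same in both blinded arms, so any such shift is expected in both.
- **That an error of 1.2 to 1.6 swamps the planned 0.796.** The first is the error in one affected subject's diary; the second is a difference between arm means. They are not comparable.

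**Conclusion.** The timing gap is real and follows directly from the text: contact on V−3, Day 1 from midnight of V−3, validity from one micturition, and division by valid days. It affects only subjects who start when reminded and do not enter the earlier episodes.

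For them the cost is under-counted episodes, added noise and possible misclassification at entry and on the responder endpoints. It is non-differential between arms and does not inflate type I error. Under the illustration (30% late, starting at 09:00 to 11:00, a void pattern of 11 per day), micturition power falls from 97% to about 95–96%. Across the wider assumed range it is 96.2% down to 89.3%. The share of late starters, the hour of contact and the void pattern are all assumptions. The case for change rests on how little the correction costs, not on a demonstrated large effect.

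**What to change.** In Protocol 5.3.1 and Table 1 footnote i, make the reminder contact on the day before diary Day 1, that is, 4 days before the scheduled visit, and have staff tell the subject to start at midnight that night. Bring SAP Table 1 footnote h, which repeats the contact timing, into line. The cost is a line of text and the same contact one day sooner. Entries made too early do no harm, because the SAP uses only the last 3 valid days before the visit.

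Do not add a primary SAP rule that makes Day 1 valid only if something was recorded before or at get-up time. It would discard complete days from subjects who did not void overnight. If overnight voids were Poisson (an assumption), that is exp(−2) = 13.5% of complete days at a mean of 2 and exp(−1) = 37% at a mean of 1. Those are low-count days, so validity could come to depend on outcome and possibly on treatment.

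If a check is wanted, make it a sensitivity analysis that excludes a Day 1 flagged as late-started by a criterion that does not depend on void counts, such as the device's entry or activation time, if that is recorded.
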